#### **Secondary Endpoints:**

- 1. Proportion of patients with complete spontaneous bowel movement response (CSBM)
- CSBM is defined as SBM that is associated with a sense of complete evacuation.
- A CSBM responder is defined as a patient with ≥3
   CSBMs per week and an increase of ≥1 CSBM per week from Baseline.
- 2. Proportion of patients with a SBM within 24 hour after the first dose of study drug
- 3. Median time to first SBM
- SBM is defined as a bowel movement that occurred in the absence of a laxative use or manual disimpaction in last 24 hours

- Baseline value for the number of SBM is defined as the average of the numbers of SBM per week for over the 2-week pretreatment Period.
- 4. Stool consistency using Bristol Stool Form Scale (BSFS)
- Change from baseline in weekly Stool Consistency using BSFS score, Time Frame: From baseline to 2 weeks
- The stool consistency is measured using the sevenpoint ordinal BSFS score.
- The BSFS classifies human stool into seven types and points them accordingly.
  - Type 1: Separate hard lumps, like nuts (hard to pass)
  - Type 2: Sausage-shaped, but lumpy
  - Type 3: Like a sausage but with cracks on its surface
  - o Type 4: Like a sausage or snake, smooth and soft
  - Type 5: Soft blobs with clear cut edges (passed easily)
  - Type 6: Fluffy pieces with ragged edges, a mushy stool
  - O Type 7: Watery, no solid pieces, entirely liquid Types 1 and 2 indicate constipation, with 3 and 4 represents the ideal stool form (especially the latter), and 5, 6 and 7 tends towards diarrhoea.
- For a given assessment week, the weekly stool consistency is defined as the sum of non-missing stool consistency score for SBMs during that week divided

- by the number of non-missing stool consistency score for SBMs during that week.
- Change From Baseline in Weekly Degree of Straining of SBMs
- The degree of straining is measured using the five-point ordinal scale (1=Not at all, 2=A little bit, 3=A moderate amount, 4=A great deal, and 5=An extreme amount).
- For a given assessment week, the weekly degree of straining is defined as the sum of non-missing straining score for SBMs during that week divided by the number of non-missing straining score for SBMs during that week.
- Change from Baseline in Weekly Abdominal Bloating Score
- The abdominal pain score is measured using the fivepoint ordinal scale (1=None, 2=Mild, 3=Moderate, 4=Severe, and 5=Very severe).
- For a given assessment week, the weekly abdominal bloating score is defined as the sum of non-missing abdominal bloating score for SBMs during that week divided by the number of non-missing abdominal bloating score for SBMs during that week.
- 7. Change from Baseline in Weekly Abdominal Discomfort Score
- The abdominal discomfort score is measured using the five-point ordinal scale (1=None, 2=Mild, 3=Moderate, 4=Severe, and 5=Very severe).
- For a given assessment week, the weekly abdominal discomfort score is defined as the sum of non-missing

	abdominal discomfort score for SBMs during that week divided by the number of non-missing abdominal discomfort score for SBMs during that week.
Criteria for Evaluation: Safety	Safety evaluations (physical examination, laboratory investigation, vital signs, and ECG parameters, adverse events and serious adverse events) will be done during the study period. Adverse events will be documented if observed, mentioned during open questioning, or when spontaneously reported.  All adverse events (AEs) will be reported, whether or not they are considered to be related to the treatment. The report of AEs will include date of onset, description of the AE, severity, relation to study medication, action taken, outcome and date of resolution.
Statistical Analysis Plan and Data handling/management	A Statistical Analysis Plan (SAP) will be prepared as a separate document and finalized before database lock. Any deviation from the original statistical plan will be described and justified in the final report, as appropriate. The procedure for accounting for missing, unused and spurious data will be included in the Statistical Analysis Plan. All statistical analysis will be conducted using SAS®, Version 9.4 or higher.  Case Report Forms (CRFs) will be used to collect information required for statistical analysis. The CRF will be designed as per protocol, protocol amendment(s). Clinical Data Management team will set up the study database / application as specified in Data Management Plan. Data will be cleaned through query generation and resolution. Medical coding,

handling of external data etc. will be done as per Data
Management Plan. Medical coding will be done by
using standard medical dictionaries like Med-DRA
and WHODD.

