# 2 weeks pretreatment period (Day -14 to Day -1) between screening and randomization

Visit 2 (Randomization visit, Day 0)

Visit 3: Week 1/ Day 7 (+2)

Visit 4: Week 2/Day 14 (+2)

Treatment	Drug Administered	No of
Group		Subjects
Intervention/Test Product	Elobixibat 5 mg tablet.*	75
Comparator	Placebo (Matching placebo oral once daily as two tablets)	75

\* Elobixibat tablet (10 mg oral once daily self-administered as two tablets of 5 mg) in patients with chronic constipation once daily for one week and then dose titration (up or down) will be done according to the patient's response.

The trial consists of three distinct periods defined as follows:

1. The screening period starts with signature of the ICF and lasts for up to 28 calendar days. During this period, patient eligibility for entry into the pretreatment period will be determined. This study includes a 2-week pre-treatment period (day -14 to -1) between screening and randomization to assess the study eligibility and baseline SBM frequency. Assessment of prohibited medications is conducted at the time of screening and accordingly if the patient meets the entry criteria assessed at the Screening Visit and does not require a washout period then patient can directly enter the pretreatment period of 14 days after screening. If the patient requires a washout period, then pretreatment period is started after the completion of wash out period. Any over-the-counter or prescription laxatives, suppositories, or enemas used to treat Chronic Constipation must not be taken during the calendar day before the start of Pretreatment period; whereas other prohibited medicines must not be taken during the 14 calendar days before the start of Pretreatment period. *The pretreatment period* is defined as the 14 calendar days immediately before randomization.

**Note:** Patients reporting more than 3 SBM during pretreatment period will be excluded from the study.

- 2. **The treatment period** begins with randomization and lasts for 2 weeks. Patients who meet all entry criteria will be randomized to treatment with 5\*mcg Elobixibat, or placebo (1:1).
- \* Elobixibat tablet (10 mg oral once daily self-administered as two tablets of 5 mg) in patients with chronic constipation once daily for one week and then dose titration (up or down) will be done according to the patient's response.

Patient will be advised to take study drug once daily in the morning before breakfast from Day 1.

[figure not shown]

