Patients will continue to provide their daily assessments, their weekly assessments, and their use of rescue medicine and any other laxatives, suppositories, or enemas up to 2 week or EOT.

A list of these assessments and the visits when they are performed is provided in the Schedule of Evaluations.

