#### 5. STUDY POPULATION

#### 5.1. Inclusion Criteria

Subjects will be enrolled in the study if they meet all the following criteria.

- 1. Male or female patients of 18-65 years age
- 2. Ambulatory patients with chronic constipation (fulfilling Rome IV criteria) reporting <3 Spontaneous Bowel Movements (SBM) per week and reports one or more of the following symptoms for the last 3 months with symptom onset at least 6 months before the Screening Visit or before starting chronic therapy with any laxative:
  - Straining during more than 25% of defecations
  - Lumpy or hard stools more than 25% of defecations
  - Sensation of incomplete evacuation more than 25% of defecations
- 3. Patients with less than 3 SBM per week during pretreatment period.
- 4. Willing to comply with protocol requirements and sign a statement of informed consent
- 5. Willing to discontinue any laxatives used before the Pretreatment period in favor of the protocol-defined Rescue Medicine (bisacodyl tablets or suppositories)
- 6. Agreed to refrain from making any new, major life-style changes that may have affected CIC symptoms (e.g., starting a new diet or changing his or her exercise pattern) from the time of signature of the ICF to the last trial visit.

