#### **6.3.2.** Secondary Efficacy variables

- 1. Proportion of patients with complete spontaneous bowel movement (CSBM)
  - CSBM is defined as SBM that is associated with a sense of complete evacuation.
  - A CSBM responder is defined as a patient with ≥3 CSBMs per week and an increase of ≥1 CSBM per week from Baseline.

- 2. Proportion of patients with a SBM within 24 h after the first dose of study drug
- 3. Median time to first SBM
  - SBM is defined as a bowel movement that occurred in the absence of a laxative use or manual disimpaction.
  - Baseline value for the number of SBM is defined as the average of the numbers of SBM per week for over the 2-week pretreatment Period.
- 4. Change from baseline in Stool consistency using Bristol Stool Form Scale (BSFS)
- Change from baseline in weekly Stool Consistency using BSFS score, Time
   Frame: From baseline to 2 weeks
- The stool consistency is measured using the seven-point ordinal BSFS score.
- The BSFS classifies human stool into seven types and points them accordingly:
  - o Type 1: Separate hard lumps, like nuts (hard to pass)
  - o Type 2: Sausage-shaped, but lumpy
  - o Type 3: Like a sausage but with cracks on its surface
  - o Type 4: Like a sausage or snake, smooth and soft
  - o Type 5: Soft blobs with clear cut edges (passed easily)
  - o Type 6: Fluffy pieces with ragged edges, a mushy stool
  - Type 7: Watery, no solid pieces, entirely liquid
- Types 1 and 2 indicate constipation, with 3 and 4 represents the ideal stool form (especially the latter), and 5, 6 and 7 tends towards diarrhoea.
- For a given assessment week, the weekly stool consistency is defined as the sum of non-missing stool consistency score for SBMs during that week divided by the number of non-missing stool consistency score for SBMs during that week.
- 5. Change from Baseline in Weekly Degree of Straining of SBMs
- The degree of straining is measured using the five-point ordinal scale (1=Not at all, 2=A little bit, 3=A moderate amount, 4=A great deal, and 5=An extreme amount).
- For a given assessment week, the weekly degree of straining is defined as the sum of non-missing straining score for SBMs during that week divided by the number of non-missing straining score for SBMs during that week.

- 6. Change from Baseline in Weekly Abdominal Bloating Score
- The abdominal pain score is measured using the five-point ordinal scale (1=None, 2=Mild, 3=Moderate, 4=Severe, and 5=Very severe).

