- For a given assessment week, the weekly abdominal bloating score is defined as
  the sum of non-missing abdominal bloating score for SBMs during that week
  divided by the number of non-missing abdominal bloating score for SBMs
  during that week.
- 7. Change from Baseline in Weekly Abdominal Discomfort Score
- The abdominal discomfort score is measured using the five-point ordinal scale (1=None, 2=Mild, 3=Moderate, 4=Severe, and 5=Very severe).
- For a given assessment week, the weekly abdominal discomfort score is defined
  as the sum of non-missing abdominal discomfort score for SBMs during that
  week divided by the number of non-missing abdominal discomfort score for
  SBMs during that week.

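### Weekly bloating and discomfort scores are averaged over SBMs only, so SBM-free days never count and the primary outcome decides which days do

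*Protocol*

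**What the plan says.** Under the secondary endpoints in the synopsis, the protocol states that "the weekly abdominal bloating score is defined as the sum of non-missing abdominal bloating score for SBMs during that week". The denominator likewise counts only the bloating scores that belong to SBMs and are not missing. Section 6.3.2 repeats this ("the sum of non-missing abdominal bloating score for SBMs during that week") and applies it to discomfort ("the sum of non-missing abdominal discomfort score for SBMs during that" week). Stool consistency and straining have the same formula in both places. In both places the bloating item also introduces its scale under another symptom's name: "The abdominal pain score is measured using the five-point ordinal scale".

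Section 4.1 says of the diary: "Patients will continue to provide their daily assessments, their weekly assessments, and their use of rescue medicine". It does not say which items are daily. Sections 7.1.2 to 7.1.4 list both scores among the diary items, without a frequency.

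On entry, section 5.1 requires "Patients with less than 3 SBM per week during pretreatment period", while a note in section 4.1 reads "Patients reporting more than 3 SBM during pretreatment period will be excluded from the study". Section 13.3.1 compares the secondary parameters by ANCOVA with the corresponding baseline value as covariate. It tests bloating and discomfort in the third gatekeeping step, by a Hochberg procedure at an overall 0.05.

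**The concern.** Stool form and straining do not exist without a movement, so a per-movement average suits them. Bloating and discomfort can be present on any day, including the days without a stool that define the condition. Under the stated rule a severely bloated day without an SBM contributes nothing. A day on which the only movement followed rescue use also drops out, because such a movement is not an SBM.

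The number of SBMs is the primary outcome, so the scores entering the average are selected by something measured after randomisation and expected to differ between arms. The arms are then compared on different kinds of days. An effect on symptoms that arises because SBM-free days become fewer cannot appear in either endpoint. Both endpoints are formally tested, so the definition bears on a confirmatory claim.

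**Working it through.** The protocol gives no figure to reproduce here. Three checks follow.

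**1. Baseline days that cannot count.** The pretreatment period is 14 days (section 4.1). The number of SBM days cannot exceed the number of SBMs.

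| Reading of the entry rule | Most SBMs in 14 days | Fewest SBM-free days |
|---|---|---|
| Under 3 per week, as a two-week average (section 5.1) | 5 | 14 − 5 = 9 (64%) |
| Not more than 3 in the whole period (section 4.1 note, read literally) | 3 | 14 − 3 = 11 (79%) |
| The same note read as up to 3 per week | 6 | 14 − 6 = 8 (57%) |

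Most baseline days are excluded on every reading.

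**2. Periods with no score.** If SBM counts are Poisson (an assumption), P(no SBM) = exp(−rate × weeks).

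| SBMs per week | Single week | Pooled 14 days |
|---|---|---|
| 1 | exp(−1) = 37% | exp(−2) = 14% |
| 1.5 | exp(−1.5) = 22% | exp(−3) = 5% |
| 2.5 | exp(−2.5) = 8% | exp(−5) = 0.7% |

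**3. What the average can and cannot show.** Let p be the share of days with an SBM, L the mean symptom level on SBM days, and L + d the mean level on SBM-free days. Suppose the drug changes only p.

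- All-days mean = L + d(1 − p), so the arm difference in change is −d × (p_drug − p_placebo).
- SBM-only mean = L in both arms and at baseline, so the arm difference is 0.

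Take 3 SBM days per week on placebo and 5.5 on elobixibat (assumed). The arms are then scored on 3/7 = 43% and 5.5/7 = 79% of days, a difference of 2.5/7 = 0.357.

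| Assumed d | All-days arm difference | Stated definition |
|---|---|---|
| 1.0 (SBM-free days worse) | −0.36 | 0.00 |
| 0.5 (SBM-free days worse) | −0.18 | 0.00 |
| −0.5 (SBM days worse) | +0.18 | 0.00 |

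With d = 1.0, rates of 2.5 against 5 also give −0.36, and 3 against 6 give −3/7 = −0.43. A simulation of 200,000 patients per arm, with 1.75 SBM days per week at baseline, agreed with these values. At 3 against 5.5 SBM days per week, a pooled 14-day baseline and one treatment week, 3.7% of placebo and 1.8% of elobixibat patients had no computable change.

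**The case against.** The strongest reply is that the consequences are unknown, and much of it stands.

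- **Direction.** A reader might infer that the definition hides a benefit. Section 1.1 says that elobixibat improves bloating, but the label information in section 1.2 lists bloating and abdominal discomfort as side effects. Symptoms could be worse on SBM days, and the sign then reverses. The zero in check 3 also follows from assuming no drug effect on SBM days.
- **Missing patients.** A reader might infer that over a third of patients fall out of the ANCOVA. The 37% is a single-week figure at 1 SBM per week. No baseline rule is stated for bloating, and the one given for SBM number averages over two weeks. Handling of missing data is left to the SAP, so loss from the analysis does not follow from the protocol.
- **Discarded data.** A reader might infer that daily scores are collected and then thrown away. The protocol does not say whether these items are recorded daily or per movement.
- **Reach.** These are the last two secondary endpoints. Stool consistency and straining also depend on having an SBM, but a rating for them has no meaning without a movement.

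None of this removes the defect. However the items are collected, a score from an SBM-free day cannot enter either endpoint. Nor can the SAP settle it: the definition is written out twice in the protocol, and an SAP that used all days would contradict it.

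**Conclusion.** The stated rule is wrong for these two endpoints and should be changed. At least 64% of baseline days cannot count under the section 5.1 criterion (57% to 79% across readings of the entry rules), and on treatment the days that count depend on the primary outcome. These two statements rest on the protocol alone.

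The share of weeks with no score rests on a Poisson assumption and on rates that the protocol does not give. The arm differences of −0.36 to +0.18 at 3 against 5.5 SBM days per week only illustrate that an effect acting through SBM-free days disappears under the stated definition. They do not predict this trial's result. The documents support no claim about the direction of bias or about how many patients the ANCOVA would lose. The abdominal pain label in the bloating item is a separate wording slip and adds nothing to this argument.

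**What to change.** In the synopsis and section 6.3.2:

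- Define the weekly bloating and discomfort scores as the mean of all non-missing daily diary ratings in the week, whether or not an SBM occurred.
- Compute each baseline the same way over the 14 pretreatment days.
- State that both items are recorded once daily.
- Keep the per-SBM average for stool consistency and straining only.
- In item 6, name the scale as the abdominal bloating score.

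The SAP should carry the same definitions. If the diary already takes these two items daily, the cost is a change of definition, with no extra visit. If it takes them per movement, the diary must be revised, and daily scores for patients already enrolled cannot be recovered.

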# LIST OF STUDY PERSONNEL:

Please refer to Section 18.2: Appendix 2

# LIST OF ABBREVIATIONS AND DEFINITIONS OF TERMS

Abbreviation	Full form	
AE	Adverse event/experience	
AGA	American Gastroenterological Association	
ANCOVA	Analysis of covariance	
BM	Bowel Movement	
BSFS	Bristol Stool Form Scale	
CC	Chronic constipation	
CBC	Complete blood count	
CDM	Clinical Data Management	
cGMP	Cyclic guanosine monophosphate	
COA	Certificate of analysis	
CRF	Case Report Form	
CRO	Contract Research Organization	
CSBM	Complete spontaneous bowel movement	
DHHS	Department of Health and Human Services	
ECG	Electrocardiogram	
eCRF	Electronic case report form	
EOT	End-of-Trial	
FDA	US Food and Drug Administration	
GC-C	Guanylate cyclase subtype C	
GI	Gastrointestinal	
IBS-C	Irritable bowel syndrome with constipation	
ICF	Informed consent form	
ICH	International Conference on Harmonization of Technical Requirements for Registration of Pharmaceuticals for Human Use	
IRB	Institutional Review Board	
ITT	Intent to treat	
NA	Not applicable	
PID	Patient identification	
PK	Pharmacokinetic	
SAE	Serious adverse event	
SBM	Spontaneous bowel movement	

SAS	Statistical analytics software.	
TEAE	Treatment-emergent adverse event	
UA	Urinalysis	

#### 1. INTRODUCTION

#### 1.1 Background

The symptoms of chronic constipation are infrequent bowel movements, straining, sensation of incomplete evacuation, and hard stools. These negatively affect quality of life (QOL) and impose a socioeconomic burden. In the absence of rectal evacuation disorders, most patients with constipation have normal colonic transit but a few have slow colonic transit associated with reduced colonic propagated contractions.

Chronic constipation (CC) is common among the elderly population. Many challenges are associated with the diagnosis and management of patients with CC. Some of these challenges arise from the current incomplete understanding of what causes constipation and from the difficulties in diagnosing and classifying the heterogeneous group of patients with CC.

The prevalence of chronic constipation (CC) among adults is approximately 15%, making it the sixth most common gastrointestinal symptom. Chronic constipation often results in visits to ambulatory clinics and gastroenterology referrals. Although the prevalence is greater in non-Caucasians than Caucasians, in women (median female to male ratio of 1.5:1), and in institutionalized rather than community-living elderly persons, symptoms can affect all ages, races, socioeconomic groups, and nationalities.

Constipation is labelled as 'Chronic idiopathic constipation (CIC)' when the cause cannot be identified. Global prevalence of CIC is 20%. Population based study from India in 505 people found the prevalence of constipation by the Rome II criteria to be 16.8% and self-reported constipation to be 24.8% in the last 1 year. Despite the availability of different treatment options for constipation, the quest for an unmet need for drugs in the treatment of patients with CC continues.

Elobixibat is a novel, minimally absorbed inhibitor of ileal bile acid transporter (IBAT; also called apical sodium-dependent bile acid transporter), which is encoded by the gene SLC10A2 expressed locally in enterocytes. An IBAT inhibitor interrupts the enterohepatic circulation of bile acids (BA) and upregulates hepatic bile acid synthesis from cholesterol. Upregulation of hepatic BA synthesis

promotes maintenance of BA pool size and may also lower serum LDL cholesterol concentrations.

Increased concentrations of bile acids in the colon enhance transit by dual actions: stimulating fluid and electrolyte secretion and inducing high-amplitude propagated contractions based on the effects of intraluminal chenodeoxycholate in the human colon.

While constipation is treated with drugs such as irritant laxatives (eg, sennoside, sodium picosulfate hydrate), saline laxatives (eg, magnesium oxide), and drugs that alter intestinal epithelial function (eg, lubiprostone), as a single agent or in combination with other drugs, the long-term use of these drugs carries the risk of developing resistance or habituation, electrolyte abnormalities including hypermagnesemia, and nausea, respectively. Elobixibat suppresses the reabsorption of bile acids in the ileum by inhibiting the IBAT, and thereby increases the amount of bile acids in the colon. As a result, secretion of fluid and electrolytes in the intestinal tract and gastrointestinal motility are enhanced.

Elobixibat showed accelerated colonic transit, looser stool consistency, decreased constipation rating, and reduced straining compared with placebo in a Phase IIa study over 14 days. Elobixibat was associated with a significantly greater increase in the number of spontaneous bowel movements (SMBs) per week from baseline to placebo. Elobixibat also improves bloating severity.

This study is planned to evaluate the efficacy, and safety of Elobixibat tablet (10 mg oral once daily administered as two tablets of 5 mg) in patients with chronic constipation once daily for one week and then dose titration (up or down) will be done according to the patient's response.

